Date Initially Completed: 3/2/2016

or Date Updated: 06/16/2017

IRB # (if known): 4831

Protocol Title:

CAN RIVAROXABAN OR APIXABAN LEAD TO ANTICOAGULATION-RELATED NEPHROPATHY?

Protocol Version/ Date:

06/16/2017

Sponsor:

Albert Einstein Society

Investigator:

[name]

Email: [contact]

Please carefully review and complete each section of this form. If your study already has a separate protocol (e.g. developed by a sponsor or submitted as part of a grant application), you have the option to reference the section and page numbers of that protocol where appropriate in this form. PLEASE NOTE: many of the questions below are looking specifically for what will be happening locally to protect participants. This information is generally not found in a protocol written for multiple sites.

NOTE: Depending on the nature of your research, certain sections below may not be applicable. Indicate "N/A" as appropriate. You must provide a response for each section. DO NOT DELETE SECTIONS OR LEAVE SECTIONS BLANK.

Keep an electronic copy of this form. You will need to modify this form when making changes to the protocol.

1) Protocol Abstract (Briefly (in 250 words or less) describe the study in language understandable to a layperson. Include a brief description of the study purpose, target disease/condition if applicable, key eligibility criteria, and main study interventions):

Anticoagulation-Related Nephropathy (ARN) is a side effect of treatment with blood thinners which leads to kidney dysfunction. ARN is diagnosed when there is a decline in kidney function after starting the blood thinner and other possible causes of this decline have been excluded. ARN has mainly been studied in relation to the common blood thinner - warfarin, where the prevalence is variable but can be as high as 37% (approximately 1 in 3) in the patients at highest risk. The risk factors that make this side effect more likely include the presence of pre-existing kidney disease, high blood pressure, older age and diabetes mellitus. Studies have shown that the occurrence of ARN can lead to an accelerated progression of pre-existing kidney disease and a 65% increase in the risk of death (mortality).

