a. Recruitment Methods:

- i. Describe when, where, and how potential subjects will be recruited (*Describe the source of subjects. Describe the methods that will be used to identify potential subjects. Describe materials, such as advertisements, that will be used to recruit subjects (include these with submission materials. If study is a chart review, describe which records will be accessed to collect data and how you will access them* : Participants will be recruited from the telemetry inpatient service and the cardiology clinic at the Einstein Medical Center Philadelphia. Participants on the telemetry inpatient service who are started on rivaroxaban or apixaban will be identified by [name] (co-investigator), a staff pharmacist who verifies new medication orders for telemetry inpatients, while participants in the cardiology clinic will be identified by the patient's cardiologist who initiates the anticoagulant in the clinic. The division of cardiology at Einstein Medical Center supports this study and all cardiologists will be informed about the study. Identified patients will be given a written description about the study and [name] (principal investigator) will be notified. All identified patients will have their medical records/chart reviewed by [name] to determine eligibility for the study. If appropriate, he will then contact them by phone and arrange a meeting to discuss the study protocol, answer any questions and complete the consent process
- ii. Will payments to subjects be provided?
 Yes, amount and timing: 4 payments of \$10 cash each at the point of each blood draw, totalling \$40 cash
 No
 N/A

b. Inclusion and Exclusion Criteria:

- i. Describe how you will screen for eligibility (e.g. review charts, perform specific screening tests, etc.): Participants will be recruited from the telemetry inpatient service and the cardiology clinic at the Einstein Medical Center Philadelphia. Participants on the telemetry inpatient service who are started on rivaroxaban or apixaban will be identified by [name] (co-investigator), a staff pharmacist who verifies new medication orders for telemetry inpatients.

Participants in the cardiology clinic will be identified by the patient's cardiologist who initiates the anticoagulant in the clinic. The division of cardiology at Einstein Medical Center supports this study and all cardiologists will be informed about the study.

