Screening will be also be carried out by a query on the electronic medical record with a confidential report generated weekly by the Einstein's AECIS which will contain all rivaroxaban and apixaban prescriptions ordered by electronic scripts. Investigators and co-investigators will review the medical records of patients on the list to determine if they meet the inclusion criteria for the study.

Identified patients will be given a written description about the study and [name] (principal investigator) will be notified. All identified patients will have their medical records/chart reviewed by [name] to determine eligibility for the study. If appropriate, he will then contact them by phone and arrange a meeting to discuss the study protocol, answer any questions and complete the consent process

- ii. Describe the criteria that define who will be included or excluded in your final study sample:

Inclusion Criteria

- Age \geq 60 years
- GFR \leq 90 ml/L based on creatinine clearance
- Participant has been initiated on long term anticoagulation with rivaroxaban or apixaban for atrial fibrillation within four weeks of recruitment
- Participant is willing to comply with all aspects of the protocol, including adherence to medical therapy and follow-up visit
- Participant is willing to give written informed consent

Exclusion Criteria

- History of blood dyscrasias or active bleeding,
- History of hematuria
- Patients on dialysis

c. Study Timelines:

- i. Duration of an individual subject's participation in the study: 6 months
- ii. Time period anticipated to enroll all study subjects or to complete chart review: 4 months
- iii. Estimated overall study duration (*i.e. from initiation to completion of primary analyses*): 12 months

d. Study Endpoints:

- i. Describe the primary and secondary study endpoints (*i.e. the outcome(s) that the study is designed to evaluate*):

Primary endpoint - Incidence of ARN is the primary outcome of this study and this is based on a documentation of AKI (defined as an increase in baseline serum creatinine \geq 0.3 mg/dL), in the absence of any other obvious etiology for the AKI identified after a standard clinical evaluation and work up by the patient's primary care physician, cardiologist or nephrologist. This incidence will be expressed as a percentage.

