Secondary endpoint - Urinalysis measurements (particularly hematuria and proteinuria) will be analyzed for correlation with the incidence of ARN. Demographic variables including age and race will be analyzed in contingency tables using Fisher's exact test to ascertain if they are significant for the primary outcome.

- ii. Describe any primary or secondary safety endpoints (*e.g. any disease or symptom that would result in the withdrawal of that subject from the study*): Subjects will be censored from the study if anticoagulation is withdrawn for any clinical reason

e. Human Research Methods:

- i. Describe and explain the study design (*e.g. randomized, double-blind, placebo-controlled clinical trial or retrospective chart review*):

This is a prospective observational study designed to determine the incidence of ARN in 40 adult patients recently initiated on rivaroxaban or apixaban at Einstein Medical Center Philadelphia.

- ii. Describe all research activities involved in this protocol, including a study visit timeline if appropriate:

Baseline demographic data, past medical history, current medication list and baseline laboratory records (taken within the last three months) will be obtained from the patient's hospital chart and the electronic medical record. Serum creatinine and urinalysis measurements will then be repeated at monthly intervals for the first three months and then at the six-month mark. These laboratory tests will be drawn at Einstein's Klein building Suite 100 by a trained phlebotomist.

If AKI, defined as an increase in baseline serum creatinine ≥ 0.3 mg/dL from baseline, is noted in any study participant, the patient and his primary care physician or cardiologist will be notified both verbally and through a detailed letter. A standard clinical evaluation and work up will then be performed by the patient's primary care physician or cardiologist as part of the patient's usual care with referral to a nephrologist if necessary. The research team will then be notified of the result of this work up.

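### Creatinine already raised when the anticoagulant is started is neither excluded nor separated from a later rise, because the baseline is not tied to the first dose

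*Protocol*

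**What the plan says.** Protocol, Study Design, item b (Inclusion and Exclusion Criteria), lists three exclusions: "History of blood dyscrasias or active bleeding", "History of hematuria" and "Patients on dialysis". The renal inclusion criterion is an upper limit of 90, expressed in "ml/L based on creatinine clearance". It has no lower limit and does not ask for a stable creatinine. The drug may have been started up to four weeks before recruitment.

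On the source of patients, item a (Recruitment Methods) states: "Participants will be recruited from the telemetry inpatient service and the cardiology clinic at the Einstein Medical Center Philadelphia". A weekly report of electronic prescriptions is a further screening route. No split between inpatients and outpatients is given.

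On baseline, item e (Human Research Methods) states: "baseline laboratory records (taken within the last three months) will be obtained". It does not say which value counts when there are several, or whether it must precede the first dose. Study creatinines follow at months 1, 2, 3 and 6. These account for all four blood draws, so no study sample is taken at entry.

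The primary endpoint (item d) is a creatinine increase of at least 0.3 mg/dL over baseline for which work-up by the patient's own physicians finds no other evident cause. The Abstract (section 1) adds an order in time: "ARN is diagnosed when there is a decline in kidney function after starting the blood thinner".

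**The concern.** An incidence is estimated in people who are free of the event at entry. Here the list screens for prior hematuria, a marker used in the secondary analysis, but not for an acute creatinine rise, which is the measurable part of the primary endpoint. A patient admitted with acutely reduced renal function and started on the drug during that admission is eligible.

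The Abstract's definition places the decline after the start of the drug, but the operational endpoint contains no such condition. Whether a pre-drug rise is counted then depends on which chart creatinine is used as baseline, and the protocol leaves that open. The error can go either way, and with 40 patients a few misclassified cases change the estimate noticeably.

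**Working it through.** **1. The protocol's own precision figures.** Inputs: n = 40 and 95% confidence (item g, Data Management). The method is the exact Clopper-Pearson interval. The upper limit U solves P(X ≤ x | 40, U) = 0.025. For x = 0 this is U = 1 − 0.025^(1/40) = 8.81%. The results are 0/40: 0 to 8.81%; 2/40: 0.61 to 16.92%; 10/40: 12.69 to 41.20%. They agree with the stated 0-9%, 0.6-17% and 13-41%. The arithmetic in the protocol is right, so the point concerns definitions only.

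**2. One patient under two permitted baselines.** Illustrative values: outpatient creatinine 1.2 mg/dL two months earlier; 1.7 on admission, before the first dose; 1.5 at month 1.
- Baseline 1.2: the admission value is already 1.7 − 1.2 = +0.5 before any drug. Month 1 is 1.5 − 1.2 = +0.3, so the AKI threshold is met although creatinine fell on treatment.
- Baseline 1.7: month 1 is 1.5 − 1.7 = −0.2, so there is no AKI. A later value must reach 1.7 + 0.3 = 2.0 to count, which is 2.0 − 1.2 = 0.8 above the patient's usual level. True ARN on the drug could be missed.

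Both baselines fit the protocol's text.

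**3. What each case does to the estimate.** One case is 1/40 = 2.5 percentage points.

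| Cases of 40 | Incidence | Exact 95% upper limit |
|---|---|---|
| 0 | 0% | 8.8% |
| 1 | 2.5% | 13.2% |
| 2 | 5.0% | 16.9% |
| 3 | 7.5% | 20.4% |

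The cited warfarin range starts at 16% in the Background and at 17% in the sample-size text. The upper limit is below 17% with at most two cases, and below 16% with at most one. The protocol states no decision rule; this benchmark is used here only to show sensitivity.

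**4. Possible number of false cases.** The documents give none of these rates, so all are assumptions: inpatient share s = 25-75%; AKI at drug start among inpatients q = 5-20%; share r = 25-100% of those who have a pre-illness baseline, still meet the threshold at a study draw, and are not attributed elsewhere. Clinic patients are taken to contribute none.
- Expected false cases = 40 × s × q × r; P(at least one) = 1 − (1 − sqr)^40.
- Low end: 40 × 0.25 × 0.05 × 0.25 = 0.125 cases, 0.3 points, P = 0.12.
- Middle: 40 × 0.50 × 0.10 × 0.50 = 1 case, 2.5 points, P = 0.64.
- High end: 40 × 0.75 × 0.20 × 1.00 = 6 cases, 15 points, P = 0.998.

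The range runs from negligible to serious, and nothing in the protocol narrows it.

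**The case against.** The strongest answer is that AKI alone is not ARN. A case also needs a work-up that finds no other evident cause, and an admission creatinine of 1.7 before any dose, falling afterwards, is just the evidence that a careful physician would use to reject the drug as the cause. The result of the work-up goes back to the study team, and nephrology referral is available. This stands in part. A reader might infer that the whole endpoint can be met before the first dose, but the documents do not support that: only the creatinine component can. The safeguard is nevertheless incomplete. It is usual care, without a common standard, carried out after the study draw, and nothing directs the physician to the creatinine at drug start.

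A reader might also infer that most recruits are inpatients, or that a particular inflation of the incidence can be stated. Neither is supported. The protocol gives no inpatient share, and the clinic and the prescription report are also sources.

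Finally, false cases would work against the hypothesis that incidence is lower than with warfarin, so they would not flatter the result. That is correct, but the primary aim is to estimate the incidence, and the other baseline choice biases it downward, towards the hypothesis.

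**Conclusion.** The point holds as a gap in both eligibility and baseline. Nothing excludes an acute creatinine rise present at drug start, no rule places the baseline relative to the first dose, and the endpoint does not enforce the order of events in the Abstract's own definition. A persisting pre-drug rise can be counted as incident ARN, or true ARN can be missed, depending on an unspecified choice of chart value.

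The net direction and size are unknown. What is firm is the leverage: 2.5 points per misclassified patient, and an upper limit that moves from 8.8% with no cases to 16.9% with two and 20.4% with three. The expected counts in the working rest wholly on assumed rates and should not be cited as estimates of the bias. Eligibility and the primary endpoint are fixed in the protocol, so the correction belongs there.

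**What to change.** 1. **Eligibility.** At the chart review already planned, exclude patients whose last creatinine before the first dose is 0.3 mg/dL or more above an earlier chart value, where one exists. A patient whose creatinine rose but returned to within 0.3 before the first dose stays eligible.
2. **Baseline and endpoint.** Define baseline as the last stable chart creatinine before the first dose, and say in advance what stable means. Count only rises of 0.3 mg/dL or more from that value that begin after the first dose. Include the pre-dose creatinine in the letter that prompts the attribution work-up.

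Use one baseline only. Keeping a different baseline and also requiring a rise of 0.3 above the last pre-dose value would set a double threshold that can lose true cases. With an earlier value of 1.2, a last pre-dose value of 1.45 and 1.70 at month 1, the rise is +0.50 from the earlier value but only +0.25 from the later one. The example also shows why stable has to be defined beforehand.

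The cost is an exclusion line, a baseline definition and an endpoint clause, with no new test. A few inpatients may be lost from the roughly 100 candidates from whom 40 are needed. One limit remains: where the chart holds only one pre-dose creatinine, the exclusion cannot be applied. The number of such patients should be reported.

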The non-vitamin K oral anticoagulants (NOACs) are a new group of drugs which have been recently approved for use as blood thinners. They have a faster onset of action compared to warfarin and unlike warfarin, they do not need frequent monitoring. Apixaban and Rivaroxaban both have a similar mechanism of action. They inhibit Factor 10 which a clotting factor. They are the most commonly prescribed NOACs at Einstein Medical Center Philadelphia. We intend to serially monitor the kidney function by measuring the serum creatinine and urinalysis of 40 high risk patients who are recently started on either apixaban or rivaroxaban over a six month period. This will enable us to discover what proportion of patients actually develop ARN after starting a NOAC.

2) Project Objectives and Hypotheses:

Determine the incidence of ARN in high risk patients on rivaroxaban or apixaban (Factor 10 inhibitors).

Hypothesis - the incidence of ARN with apixaban or rivaroxaban is less than the previously reported incidence of ARN in warfarin.

- Describe demographic and urinalysis-associated predictors of ARN in patients on rivaroxaban or apixaban (Factor 10 inhibitors)

3) Background/Significance of Research (*Provide the scientific or scholarly background and rationale for the research based on the existing literature (include references). Describe relevant prior experience and gaps in current knowledge. Describe any relevant preliminary data. Explain the significance of the research in terms of why it's important and how it will add to existing knowledge.*):

Anticoagulation-related nephropathy (ARN) is an understudied renal complication of anticoagulant therapy that is characterized by acute kidney injury (AKI) defined as an increase in baseline serum creatinine ≥ 0.3 mg/dL, without any alternate etiology, in the setting of a supra-therapeutic International Normalized Ratio (INR) greater than 3.0 [1-7]. ARN has mainly been studied in relation to warfarin, it usually occurs in the first two months of starting anticoagulant therapy and retrospective studies have estimated the prevalence to range from 16% to 37% [4-6]. The strongest risk factor for ARN is pre-existing chronic kidney disease (CKD); other risk factors include older age, diabetes mellitus and hypertension [1,4]. Patients with ARN have an accelerated progression of CKD and a retrospective study of more than 15,000 patients on warfarin showed a 65% increase in mortality in patients with ARN [4,6].

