The clinical trials that compared the NOACs to warfarin did not specifically study ARN and did not repeat creatinine and urinalysis testing in the first two to three months of therapy to establish possible ARN diagnosis [15-20]. In most of these studies, only baseline creatinine and creatinine levels 6 to 12 months later were analyzed, hence it is possible that ARN was under-diagnosed as most cases of ARN are detected in the first eight weeks of therapy. Our study aims to accurately capture ARN cases by making these measurements monthly in the first three months of starting the anticoagulant.

This study is pivotal because it will for the first time, define the incidence of ARN in patients on rivaroxaban or apixaban therapy. If we find that ARN incidence in patients started on rivaroxaban or apixaban is less than that seen with warfarin, this can help support evidence that this NOAC is safer for the kidneys compared to warfarin and this data can enable us make evidence based decisions regarding the continued use of the medication to help our patients. If on the other hand we find that the medication leads to ARN, then we will be contributing important post-marketing surveillance data that can also help us make safety decisions about the use of the medication in the future.

INNOVATION

Previous studies on ARN have utilized retrospective study designs which have many epidemiological pitfalls including the cause versus effect bias and the inability to ascertain relative risk [1]. Our study is unique because we intend to utilize a prospective epidemiological design to study this renal complication, a first in the study of ARN. This is important because ARN is a diagnosis of exclusion and hence a prospective study is able to more accurately define cases of the condition compared to the assumptions that are made in retrospective studies where further work up cannot be done in retrospect.

This will be the first epidemiological study focused on ARN in a NOAC. Even though NOACs are new, they are becoming ubiquitous and a mainstay in clinical practice and not just an alternative to warfarin. For example, the recent CHEST guidelines recommend them as first line therapy in the treatment of venous thromboembolism [8]. Hence it will be important to clearly delineate their effects on the kidneys.

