- i. Describe steps that will be taken to secure the data (e.g. training, authorization of access, password protection, encryption, physical controls, certificates of confidentiality and separation of identifiers and data) during storage, use and transmission: As stated above, a study participant list containing identifiable data will be password protected and stored on the Einstein system. This list will only be able to be accessed by members of the research team. All other data will be stored in a separate database with unique but unidentifiable identification numbers. At the termination of the study the initial study participant list will be deleted.
- ii. Describe the data analysis plan, including any statistical procedures and method for determining the sample size for the study:

Incidence of ARN is the primary outcome of this study and this is based on a documentation of AKI (defined as an increase in baseline serum creatinine ≥ 0.3 mg/dL), in the absence of any other obvious etiology for the AKI identified after a standard clinical evaluation and work up by the patient's primary care physician, cardiologist or nephrologist. This incidence will be expressed as a percentage.

Urinalysis measurements (particularly hematuria and proteinuria) will be analyzed for correlation with the incidence of ARN. Demographic variables including age and race will be analyzed in contingency tables using Fisher's exact test to ascertain if they are significant for the primary outcome.

There is no data at all in the literature for the incidence of ARN with rivaroxaban or apixaban and we short-listed that number (40) based on the reported incidence for warfarin (17-37%). We are selecting the patients at highest risk (elderly, CKD) for anticoagulation-related nephropathy (ARN) and we expect that the incidence we obtain will be the highest for the population we are studying.

In terms of precision, we will calculate confidence intervals of the proportional incidence using Stata (command line `cii 40 (incidence)`). If the incidence is zero, Stata calculates the 95% confidence interval based on our sample size as 0-9%. If we only find 2 cases of ARN, Stata calculates the point estimate incidence at 5% with 95% confidence interval as 0.6% - 17%, If we find 10 cases of ARN, Stata calculates the point estimate incidence as 25% with 95%

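### The AKI criterion has no onset or rate window, and only an unstandardised search for other causes keeps gradual CKD progression out of the ARN percentage

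*Protocol*

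**What the plan says.** The primary endpoint (Study Design, d(i), repeated in the data analysis plan, g(ii)) has two parts.

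- **Creatinine.** "Incidence of ARN is the primary outcome of this study and this is based on a documentation of AKI", with AKI "defined as an increase in baseline serum creatinine ≥ 0.3 mg/dL". The same threshold appears in e(ii) and e(iii). None of these places gives a rate of rise, an onset window or a rule for gradual change.
- **Etiology.** The AKI must stand "in the absence of any other obvious etiology for the AKI identified after a standard clinical evaluation and work up". Under e(ii) the patient's own physician does this work-up "as part of the patient's usual care with referral to a nephrologist if necessary", and the research team is told the result.

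Baseline comes from "baseline laboratory records (taken within the last three months"). Creatinine is then "repeated at monthly intervals for the first three months and then at the six-month mark". All cases go into one percentage.

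On timing, the Background says of ARN under warfarin that "it usually occurs in the first two months of starting anticoagulant therapy". The Significance text says that most cases are detected within eight weeks and gives the purpose of the schedule: "Our study aims to accurately capture ARN cases by making these measurements monthly in the first three months of starting the anticoagulant". Section 5(a) describes the target population as elderly patients with CKD.

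**The concern.** The word acute in the endpoint has no operational content beyond the 0.3 mg/dL threshold. With the oldest permitted baseline and a first rise at the last draw, the change may have built up over about nine months. In patients with CKD, a steady decline can reach the threshold without any acute event.

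The etiology clause is then the only filter, and it is weakest for this kind of case. Different physicians apply it in usual care, no adjudication rule is given, and the text is silent on whether progression of already known CKD is another obvious etiology. If no other cause is recorded, the rise is counted as ARN. Month 6 is also the last draw, so no later study value can show whether a rise first seen there was acute or progressive.

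What is at stake is the reading of the single percentage. It may combine the early injury that the rationale describes with slow progression, and the reported result would not show in what proportion.

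**Working it through.** **1. The protocol's own figures.** Exact (Clopper-Pearson) 95% limits for x cases of n = 40 are the Beta quantiles at 0.025 with parameters (x, n−x+1) and at 0.975 with parameters (x+1, n−x); for x = 0 the lower limit is 0.

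| Cases | Computed | Stated in g(ii) |
|---|---|---|
| 0 | 0–8.8% | 0–9% |
| 2 | 0.6–16.9% | 0.6–17% |
| 10 | 12.7–41.2% | 13–41% |

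The stated intervals reproduce.

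**2. Longest span of a counted rise.** Baseline up to 3 months old plus draw at month 6: 3 + 6 = 9 months. For a rise first seen at month 3: 3 + 3 = 6 months. There is no draw between months 3 and 6.

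**3. Decline needed to reach +0.3 mg/dL.** Assume creatinine is inversely proportional to clearance. From baseline b, the fractional loss is 0.3 / (b + 0.3). The clearances are illustrative (creatinine × clearance about 67) and are not in the document. The annual rate is the loss divided by 0.75 year.

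| Baseline (mg/dL) | Assumed clearance (mL/min) | Fraction lost | Loss (mL/min) | Per year over 9 months |
|---|---|---|---|---|
| 1.0 | 67 | 23% | 15.5 | 21 |
| 1.5 | 45 | 17% | 7.5 | 10 |
| 2.0 | 33 | 13% | 4.3 | 5.7 |
| 2.5 | 27 | 11% | 2.9 | 3.9 |

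Slow decline meets the threshold readily only when baseline function is already poor. Eligibility runs up to a GFR of 90, so the exposure depends on a case mix that the protocol does not give.

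**4. How often the creatinine criterion could first be met at month 6 with no ARN.** This is a simulation with 400,000 draws per scenario, one noisy baseline, visits at months 1, 2, 3 and 6, and linear GFR loss over six months from a baseline taken at time zero. The inputs are assumed: true baseline 1.2–2.0 mg/dL, within-person CV 5–10%, GFR loss 0–10%. The chance per patient ranges from about 0 to 21%. At baseline 1.5 mg/dL and CV 8%:

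| GFR loss in 6 months | First met by month 3 | First met at month 6 | Month-6 firsts among 40 |
|---|---|---|---|
| 0% | 9.4% | 2.1% | 40 × 0.021 = 0.8 |
| 5% | 13.0% | 6.0% | 40 × 0.060 = 2.4 |
| 10% | 17.7% | 13.9% | 40 × 0.139 = 5.6 |

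These are flags before any etiology work-up. For the given inputs they are therefore a ceiling on miscounted ARN, not an estimate of it. The month-6 share grows with drift. The flags by month 3 with no GFR loss are variability alone, which a split by visit does not address.

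**5. Late unrelated rises.** If these occur at an assumed rate r per month, months 3 to 6 yield 1 − (1 − r)³: 1.5%, 3.0% and 5.9% for r = 0.5%, 1% and 2%, or 0.6, 1.2 and 2.4 of 40. This too is a ceiling at those rates, because it supposes that the work-up excludes none.

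**6. What each retained case does.** 1/40 = 2.5 points.

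| Cases | Incidence (exact 95% CI) |
|---|---|
| 2 | 5.0% (0.6–16.9%) |
| 3 | 7.5% (1.6–20.4%) |
| 4 | 10.0% (2.8–23.7%) |
| 6 | 15.0% (5.7–29.8%) |

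Going from 2 to 3 cases moves the upper limit from just below to above 17%, the lower end of the warfarin range quoted in g(ii). The protocol states no formal comparison rule, so this only illustrates scale.

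**The case against.** A reader might infer that there is no time limit at all and that late unrelated rises count exactly like early ARN. The document does not support that. A rise with an obvious other cause is excluded at any visit, follow-up ends at six months, and nine months is the extreme case.

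A reader might also infer that dropping the INR above 3.0, which is part of the Background definition, removed a time anchor. It did not. That is a criterion of drug effect, the Background definition has no window either, and the protocol notes that these drugs need no dose-response monitoring.

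Nor is there a contradiction on onset. The text says that ARN usually occurs early and that most cases are detected early, not that all are. Six-month incidence on treatment is a legitimate target. Making month 3 the headline would be a preference, and it would not remove drift: a month-3 rise can still span six months. On the scale in step 3, a patient at 2.5 mg/dL losing 2.9 mL/min in that time (5.8 per year) would be counted as early.

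The error also runs in one direction. Miscounted progression raises the incidence, which works against the hypothesis of a lower rate than with warfarin. But the protocol also intends to use a positive finding as safety data, and there inflation misleads.

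Finally, tabulation by visit is often left to a SAP. That has force for the table, but not for the endpoint definition, which this protocol fixes itself. What remains is narrow: the criterion has no window, and the one filter does not say how to treat progression of known CKD.

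**Conclusion.** The point holds in this limited form. A gradual rise can satisfy the AKI criterion and, if no other obvious cause is recorded, becomes ARN by default, while the rationale centres on injury in the first two to three months. Each such case adds 2.5 percentage points. The number of such cases cannot be derived from the document. The ranges in steps 3 to 5 rest on assumed baseline creatinine, variability, decline and event rates, and those in steps 4 and 5 are taken before etiology exclusion. The six-month incidence need not be abandoned, but as one undivided figure it supports less than the protocol wants from it. The change should be made, and it is inexpensive.

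**What to change.** In the endpoint text, d(i), and the data analysis plan, g(ii):

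1. Keep the six-month ARN incidence with its exact 95% interval. Report it also split into cases first seen by the month-3 draw, the window that the rationale targets, and cases first seen only at month 6. For example, 4 cases in all with 2 seen by month 3 would read 10.0% (2.8–23.7%) to six months and 5.0% (0.6–16.9%) by month 3.
2. State that gradual progression of known CKD counts as an alternative etiology when cases are classified.
3. Add a sensitivity count that excludes gradual rises, judged from the serial creatinine values. One possible rule excludes a first rise at month 6 that is less than 0.3 mg/dL above the month-3 value.

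The rule in item 3 is imperfect. It still spans three months, and it would drop an acute late event that adds 0.2 mg/dL to an earlier 0.1 mg/dL rise. It therefore belongs in a sensitivity count and not in the primary definition.

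The notification trigger and the clinical work-up stay unchanged. The cost is a few sentences and one or two table lines from values already collected. The small downside is that some true late ARN may leave the sensitivity count, though it stays in the six-month figure.
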